10.5 Safety Subgroup Analysis

Concomitant immunomodulator use at Study M06-806 baseline defined in Section 7.3 and concomitant corticosteroid use will be used in subgroup analysis for incidence of treatment-emergent serious infections. The incidence of treatment-emergent serious infections and rates of serious infections per patient years for subjects who received adalimumab monotherapy compared with subjects who received adalimumab plus immunomodulators will be summarized. In addition to the analysis of serious infections, the two subgroups (adalimumab monotherapy and adalimumab plus immunomodulators) are further stratified by concomitant corticosteroid use.

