4.5 Derived, Defined and Transformed Variables

For the analysis the following efficacy variables are defined:

1. The clinical remission and response as per PCDAI (to be measured for all subjects) are defined as follows:
 - Clinical response is defined as a decrease from Study M06-806 Baseline in PCDAI ≥ 15 points.
 - Clinical remission is defined as PCDAI ≤ 10 .
2. The clinical remission and response as per CDAI (to be measured and analyzed only for subjects 13 years and older at Study M06-806 Baseline) are defined below:
 - Clinical response is defined as a decrease from Study M06-806 Baseline in CDAI ≥ 70 points.
 - Clinical remission is defined as CDAI < 150 .
3. The corticosteroid-free remission as per PCDAI (to be measured for all subjects with corticosteroid use at Study M06-806 Baseline) is defined as follows:
 - Discontinued corticosteroids for at least 90 consecutive days prior to the respective visit and PCDAI ≤ 10 at that visit.

4. The corticosteroid-free remission as per CDAI (to be measured and analyzed only for subjects 13 years and older at Study M06-806 Baseline with corticosteroid use at Study M06-806 Baseline) is defined as follows:
 - Discontinued corticosteroids for at least 90 consecutive prior to the respective visit and CDAI < 150 at that visit.
5. The concomitant corticosteroid-free remission as per PCDAI (to be measured for all subjects with corticosteroid use at Study M06-806 Baseline) is defined as follows:
 - Discontinued corticosteroids prior to the respective visit and PCDAI \leq 10 at that visit.
6. The concomitant corticosteroid-free remission as per CDAI (to be measured and analyzed only for subjects 13 years and older at Study M06-806 Baseline with corticosteroid use at Study M06 806 Baseline) is defined as follows:
 - Discontinued corticosteroids prior to the respective visit and CDAI < 150 at that visit.

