7.3 Previous Treatment and Concomitant Medications

Previous medications and concomitant medications will be coded by WHO DRUG dictionary. The number and percentage of subjects who had taken medications will be summarized by generic drug name for the ITT population. Previous medications taken prior to the first dose of the previous Study M06-806 will be summarized. Concomitant medications taken during Study M06-807 will be summarized.

Concomitant immunomodulator use at Study M06-806 baseline is defined as the use of immunomodulators [6-mercaptopurine (6-MP), azathioprine (AZA), and methotrexate

(MTX)] if the medication start date was before or equal to adalimumab first dose date and the medication end date was after or equal to adalimumab first dose date. The study required that subjects stayed on concomitant immunomodulators at least through Week 26 in Study M06-806 if they were using those immunomodulators at Study M06-806 baseline. After Week 8, decreases in the dose or discontinuation of Crohn's related concomitant treatments were allowed according to the investigators' medical judgment. Subjects who were in flare or who flared after they had reduced or completely tapered their dose of corticosteroid could have their corticosteroid dose increased or restarted at the discretion of the investigator.

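### Section 10.5 groups serious infections by immunomodulator use on a single date but describes the groups as treatment received; the corticosteroid stratum is undated and the event window is stated in two ways

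*SAP*

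**What the plan says.** Section 10.5 names its grouping variables: "Concomitant immunomodulator use at Study M06-806 baseline defined in Section 7.3 and concomitant corticosteroid use will be used in subgroup analysis". The next sentence describes the groups as "subjects who received adalimumab monotherapy compared with subjects who received adalimumab plus immunomodulators", and gives both incidence and rates per patient-years. The two groups are then split again by concomitant corticosteroid use, with no date or rule.

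Section 7.3 limits immunomodulators to 6-MP, azathioprine and methotrexate. A subject counts as a user "if the medication start date was before or equal to adalimumab first dose date" and the end date is on or after that same date. The drug had to be kept "at least through Week 26 in Study M06-806". The section continues: "After Week 8, decreases in the dose or discontinuation of" Crohn's-related treatment was left to the investigator's judgment; it does not name the study to which this Week 8 belongs. Subjects in flare "could have their corticosteroid dose increased or restarted at the discretion of the investigator".

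Section 6.0 starts treatment-emergent events at the first M06-807 injection. Section 10.2 starts them at the first dose in M06-806. Both end 70 days after the last M06-807 dose.

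**The concern.** A rate per patient-year in subjects described as having received combination therapy reads as the rate while on both drugs. The definition does not deliver that. It fixes membership on one day, and nothing in Section 10.5 ends the combination group's person-time when the immunomodulator stops.

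This is the SAP's only planned summary of serious infections by combination therapy. The other material gives context only. Section 7.3 says "Concomitant medications taken during Study M06-807 will be summarized", and Section 10.2 lists events by subject, but neither relates an infection to immunomodulator status when it occurred.

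Two further gaps affect the same table. Without a corticosteroid time point, the programmer has to choose who is in each stratum. With two event windows, both numerator and denominator of the rate depend on which section is followed.

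**Working it through.** The SAP gives no figure for this table, so there is none to reproduce. The check asks how much of a baseline user's counted time could be off the drug.

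**Inputs**
- M06-806 length: 52 weeks (Section 3.1).
- Maximum M06-807 duration: 408 weeks (Section 4.2).
- Tail after last dose: 70 days = 10 weeks (Sections 6.0 and 10.2).
- Required immunomodulator use: to Week 26 of M06-806 (Section 7.3).
- Assumed: shorter M06-807 durations of 48, 96 and 192 weeks, and that the Week 8 in Section 7.3 is Week 8 of M06-807.

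**Formulas**, with f = weeks from first to last M06-807 dose
- Section 6.0 window: f + 10.
- Section 10.2 window: 52 + f + 10 = 62 + f.
- Case A, stop at Week 26 of M06-806: on-drug share 0/(f + 10) or 26/(62 + f).
- Case B, stop at Week 8 of M06-807: on-drug share 8/(f + 10) or (52 + 8)/(62 + f) = 60/(62 + f).

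| f (weeks) | A, Section 6.0 | A, Section 10.2 | B, Section 6.0 | B, Section 10.2 |
|---|---|---|---|---|
| 48 | 0% | 26/110 = 23.6% | 8/58 = 13.8% | 60/110 = 54.5% |
| 96 | 0% | 26/158 = 16.5% | 8/106 = 7.5% | 60/158 = 38.0% |
| 192 | 0% | 26/254 = 10.2% | 8/202 = 4.0% | 60/254 = 23.6% |
| 408 | 0% | 26/470 = 5.5% | 8/418 = 1.9% | 60/470 = 12.8% |

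These are limits for one subject. A subject who never stops is at 100%. In case A with f = 408, 470 − 26 = 444 weeks off the drug would be counted as combination therapy.

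**What dilution could do (assumed rates only).** Suppose the rate is 6 per 100 patient-years on an immunomodulator and 3 off it, and a share p of the combination group's time is off drug. The reported ratio is [6(1 − p) + 3p]/3. For p = 0, 0.25, 0.50, 0.75 and 0.90 this is 2.00, 1.75, 1.50, 1.25 and 1.10. In practice subjects stop for reasons that may relate to infection risk, so the direction is not assured.

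**Corticosteroid stratum.** Two readings are plausible.
- *M06-806 baseline.* Section 4.5 defines its corticosteroid-free endpoints as "to be measured for all subjects with corticosteroid use at Study M06-806 Baseline", and Sections 7.1, 11.2 and 11.4 also use baseline status.
- *Any use during M06-807.* This is the period over which Section 7.3 summarizes concomitant medication.

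A subject on corticosteroids at M06-806 baseline who tapered off before M06-807 and did not restart is a user on the first reading and a non-user on the second. The Section 7.3 date rule does not settle this, because it covers immunomodulators only.

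**Event window.** A serious infection during the 52 weeks of M06-806 counts under Section 10.2 and not under Section 6.0. Section 10.5 does not say which applies or how its patient-years are counted. The only duration the SAP defines, treatment exposure in Section 9.0, covers M06-807 alone.

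**The case against.** The grouping is disclosed. Section 10.5 names the M06-806 baseline and points to an exact date rule, so the later wording can be read as shorthand for groups already defined. Grouping at baseline is also legitimate, since it avoids assigning subjects by decisions made after treatment began. Both points stand, and for that reason the grouping should be kept. They do not rescue the description, because a patient-year rate for subjects said to have received combination therapy implies exposure that the rule does not check.

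The percentages are not evidence of misclassification. Week 26 is a minimum, the SAP does not report that any baseline user stopped, and the protocol's rules for adjusting Crohn's medication were not available to this review. This stands in full.

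On corticosteroids, the phrase locating use at M06-806 baseline might be carried over to both variables, and the SAP's other corticosteroid groupings use baseline. That makes baseline the likelier intention, but the text does not fix it. A reader might infer a third reading, status at each visit, from the concomitant corticosteroid-free remission endpoint in Section 4.5. That is strained: the endpoint belongs to a visit, and infections do not.

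The window conflict reaches beyond this table. It matters here because it sets how much on-drug time the baseline groups contain and which infections are counted.

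**Conclusion.** The point holds as a mismatch between definition and description, with two unsettled inputs. Followed as written, Section 10.5 can report off-drug time and infections as combination therapy, can stratify the same subject differently on two fair readings of corticosteroid use, and can compute its rate over either of two windows.

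The size is unknown. The on-drug shares, from 0% up to 54.5% in the cases shown, are per-subject limits that rest on the earliest permitted stop, on assumed follow-up below 408 weeks and, in case B, on the assumed meaning of Week 8. A reader might infer that the combination-therapy rates are biased by a known amount, or that grouping at baseline is invalid. The SAP supports neither: it gives no number of stoppers, and the direction of any bias is uncertain.

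Sections 10.1 and 11.3 rule out statistical tests, so no error rate is affected. The harm is that readers attribute infection rates to the wrong exposure. The changes should be made before the table is produced.

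**What to change.** 1. Keep the baseline grouping and label it *immunomodulator use at M06-806 baseline: yes/no*, in line with the baseline labels in Section 11.4. Drop the description of treatment received.
2. Fix the corticosteroid stratum at one stated time point, such as M06-806 baseline.
3. Reconcile Sections 6.0 and 10.2, and use the same window for events and person-time in Section 10.5.
4. Report how many baseline users stopped immunomodulators, and when.

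Items 1 to 3 are wording and one definition. Item 4 needs modest programming from the medication start and stop dates that the Section 7.3 rule already uses.

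Optional: a supportive split of events and person-time by actual immunomodulator status, with any lag fixed in advance. With 100 enrolled subjects the cells will be sparse, some subjects will contribute to both, and the reason for stopping may confound the comparison. It would be read beside the baseline table, and omitting it is not an error.

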11.0 Efficacy Analysis

11.1 General Considerations

For the analysis, the efficacy for the ITT population will be evaluated by number and percent of subjects with clinical remission, response (as per CDAI and PCDAI), corticosteroid-free remission (per PCDAI and CDAI), concomitant corticosteroid-free remission (per PCDAI and CDAI), and summary of the CDAI and PCDAI over time.

No inferential analysis will be performed for this open-label study. Analysis will be only descriptive summaries, and will be presented for the ITT population. Results will be presented for all subjects as one group. In general, CDAI and PCDAI will be summarized by the mean, standard deviation, minimum, median, and maximum; and clinical

remission/response and corticosteroid-free remission will be summarized by number and percent of subjects in remission and response over time.

Efficacy summaries will be presented based on the derived visits discussed in Section 6.0.

11.2 Efficacy Analysis

For subjects with corticosteroid use at Study M06-806 Baseline, the number and percent of them with corticosteroid-free remission and concomitant corticosteroid-free remission (per PCDAI and CDAI, as defined in Section 4.5) over time will be summarized.

Change from Baseline in total IMPACT III over time for patients at least 10 years old at Baseline, change from Baseline in WPAI scores over time, change from Baseline in "z" scores for height over time and change from Baseline in BMI over time will be summarized.

In addition, change from Baseline in hsCRP levels over time will be summarized. Due to a technical issue a number of blood samples were affected by an under-recovery of hsCRP. All hsCRP values will be kept in the database as initially reported and will be analyzed as such in the primary analysis. Additional sensitivity analyses will be performed to account for hsCRP values of affected samples as follows:

- all affected values will be considered as missing values in an observed case analysis.
- all affected values will be imputed using LOCF rule.

For Health Care Resource Utilization (HCRU), cumulative HCRU including number of physician visits; number of emergency room visits; number of hospital admissions; total number of days in hospital will be summarized for the ITT population. And the ratio of the total number of utilizations and the total time under observation will be calculated across all subjects. HCRU will be analyzed as observed only.

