3.1 Scope of the Analysis

The first interim analysis was completed using data on or before 30 November 2010 to obtain preliminary results on the longer term safety and efficacy of adalimumab in pediatric Crohn's disease (CD), beyond the 52 weeks of the parent Study M06-806. The principal purpose of the first interim analysis was to evaluate the safety of the study drug. The efficacy variables, clinical remission and clinical response based on Pediatric Crohn's Disease Activity Index (PCDAI) and Crohn's Disease Activity Index (CDAI) were summarized over time. Information on demographic, baseline characteristics and prior/concomitant medications of the enrolled subjects were also provided.

The second interim analysis was performed using data on or before 31 July 2011. Similar variables on safety, efficacy, demographic, baseline characteristics and prior/concomitant

medications of the enrolled subjects were provided. In addition, the dose de-escalation population which consists of all subjects who have responded well to treatment and had dose and/or frequency decrease per protocol Amendment 4 were examined.

The third interim analysis was performed using data with an associated cutoff date of 31 January 2015. In addition to the analyses performed in the second interim analysis, corticosteroid-free remission and concomitant corticosteroid-free remission were added as new efficacy variables. Subgroup analysis was conducted on some safety and efficacy variables.

The final analysis will be performed using final data.

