Subjects may have been allowed to decrease prednisone (or equivalent) and budesonide if qualifications were met (Section 5.2.3.2 of protocol for required timing and rate of taper).

Subjects may have been allowed to adjust their Crohn's specific concomitant medications as specified in Section 5.2.3.2 of protocol.

The duration of the study could last up to 408 weeks (approximately 8 years). Subjects who completed, or who early terminated from the study were to be contacted 70 days after their last dose of study drug to obtain information on any ongoing and new adverse events.

This study was to be concluded approximately 12 weeks after the following criteria were satisfied:

- Study drug received country and local (if applicable) regulatory approval for pediatric Crohn's Disease.
- All applicable local reimbursement procedures were completed.

[figure not shown]
Sites were notified once these criteria were met.

Following country and local (if applicable) regulatory approval and applicable local reimbursement approval of the study drug in a country, subjects should have returned to their next scheduled study visit as specified in the protocol. The termination visit should have been conducted in place of their regular scheduled study visit. These subjects should have been considered as having completed the study.

[figure not shown]
After completion of Study M06-806 and consideration of efficacy, safety and population pharmacokinetic results in conjunction with exposure-response modeling and simulation, it was observed that both the Low-Dose and High-Dose treatment provided evidence of efficacy and safety. Therefore, in order to minimize the systemic exposures to study drug to the lowest doses necessary in children with CD, Amendment 4 provided investigators with the option of dose de-escalation by reducing the dose or switching from ew to eow based on the clinical status of the individual patient. In addition, since the 10 mg eow dose was efficacious in subjects weighing < 40 kg in Study M06-806 patients had the option to be switched to this dose based on their body weight and clinical status at the discretion of the investigator. Subjects who experienced a disease flare may have re-increased their dosage or dose frequency to the next higher treatment level regardless

of prior dose or dose frequency decrease. A schematic of the study design is shown in [Figure 1](#) (prior to Amendment 4) and in [Figure 2](#) (after Amendment 4).

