6.0 Analysis Conventions

Definition of Baseline

For the analysis of change and percent change, the baseline value for a variable is defined as the last non-missing value on or before the date of the first dose of study medication during the parent Study M06-806. Clinical response and remission based on CDAI and PCDAI will also be calculated using the Study M06-806 baseline values. The baseline values of the Study M06-806 will be reported for the subjects enrolled in the Study M06-807.

However, as mentioned in the next section, the visit windows used for the analysis are defined with respect to the first dose date during the Study M06-807.

Definition of Rx Days (Days Relative to the First Dose During Study M06-807)

Rx days are calculated for each time point relative to assigned visit. They are defined as the number of days between the day of the first dose of study drug in Study M06-807 and the specific time point. Rx days are negative values when the time point of interest is prior to the first study drug dose day. Rx days are positive values when the time point of interest is after the first study drug dose day. The day of the first dose of study drug in Study M06-807 is defined as Rx Day 1, while the day prior to the first study drug dose is defined as Rx Day -1 (there is no Rx Day 0).

Definition of Analysis Windows

All time points and corresponding time windows are defined based on Rx days. If more than one assessment is included in a time window the assessment closest to the nominal day should be used. If there were more than one observation with equal distance to the nominal day the latest one will be used in the analyses. For efficacy related analyses, if multiple measurements for a particular parameter are collected on the same day for the same subject, the average of those measurements will be used. For safety related analyses, if multiple measurements are made for a particular laboratory or vital sign parameter on the same day for the same subject, the average of the values will be used in

the analyses. For summaries and listings of shift from baseline and potentially clinically significant values all values will be considered in the analyses.

Table 2. Time Window for Measurements Done at Each Office Visit

Assigned Visit	Nominal Day	Time Window (Rx Day Range)
Week 0	1	≤ 1
Week 4	29	2 – 43
Week 8	57	44 – 71
Week 12	85	72 – 127
Week 24	169	128 – 211
Week 36	253	212 – 295
Week 48	337	296 – 379
Week 60	421	380 – 463
Week 72	505	464 – 547

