Week 84	589	548 – 631
Week 96	673	632 – 715
Week 108	757	716 – 799
Week 120	841	800 – 925
Week 144	1009	926 – 1093
Week 168	1177	1094 – 1261
Week 192	1345	1262 – 1429
Week 216	1513	1430 – 1597
Week 240	1681	1598 – 1765
Week 264	1849	1766 – 1933
Week 288	2017	1934 – 2101
Week 312	2185	2102 – 2269
Week 336	2353	2270 – 2437
Week 360	2521	2438 – 2605
Week 384	2689	2606 – 2773
Week 408	2857	2774 – 2941

Table 3. Time Window for Analysis of IMPACT III

Assigned Visit	Nominal Day	Time Window (Rx Day Range)
Week 0	1	≤ 1
Week 12	85	2 – 127
Week 24	169	128 – 253
Week 48	337	254 – 421
Week 72	505	422 – 631
Week 108	757	632 – 799
Week 120	841	800 – 925
Week 144	1009	926 – 1093
Week 168	1177	1094 – 1261
Week 192	1345	1262 – 1429
Week 216	1513	1430 – 1597
Week 240	1681	1598 – 1765
Week 264	1849	1766 – 1933
Week 288	2017	1934 – 2101
Week 312	2185	2102 – 2269
Week 336	2353	2270 – 2437
Week 360	2521	2438 – 2605
Week 384	2689	2606 – 2773
Week 408	2857	2774 – 2941

Table 4. Time Window for Analysis of hs-CRP

Assigned Visit	Nominal Day	Time Window (Rx Day Range)
Week 0	1	≤ 1
Week 24	169	2 – 253
Week 48	337	254 – 421
Week 72	505	422 – 631
Week 108	757	632 – 883
Week 144	1009	884 – 1177
Week 192	1345	1178 – 1429
Week 216	1513	1430 – 1681
Week 264	1849	1682 – 1933
Week 288	2017	1934 – 2101
Week 312	2185	2102 – 2269
Week 336	2353	2270 – 2437
Week 360	2521	2438 – 2605
Week 384	2689	2606 – 2773
Week 408	2857	2774 – 2941

The time window for treatment-emergent adverse events is from the day of the first injection of Study M06-807 study drug to the last non-missing injection date + 70 days.

Definition of Missing Data Imputation

Baseline Value is Missing: Subjects will be excluded from analysis of change and percent change from baseline if baseline evaluation (Baseline of Study M06-806) is missing.

Missing Efficacy and Outcome Evaluations: The following imputation methods will be used to impute missing values in the efficacy analyses. In addition, an observed case analysis will be performed.

When an endpoint in the study is analyzed as observed (this is denoted as Observed Case [OC]), no imputation of the missing values will be performed.

In the subgroup analysis of efficacy variables, Last Observation Carried Forward (LOCF) analysis will also be carried out as sensitivity analysis. The following rules will be used for the LOCF approach:

1. Baseline (the Week 52 visit of Study M06-806) and pre-baseline values will not be used to impute the missing post-baseline values.

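### BMI is summarised as raw change from the M06-806 baseline while height, in the same sentence, is a z-score, so the BMI summary can include normal growth and may be misread as nutritional benefit

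*SAP*

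**What the plan says.** Section 11.2 of the SAP lists several changes from baseline in one sentence. Height enters through z-scores ("scores for height over time"). The next item is BMI: "change from Baseline in BMI over time will be summarized". The words for change from baseline are repeated before BMI, so the z-score does not carry over to it. Section 7.1 lists BMI in kg/m², and no BMI z-score, percentile or growth reference appears anywhere in the SAP.

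For analyses of change, Section 6.0 defines baseline as "the last non-missing value on or before the date of the first dose of study medication during the parent Study M06-806". Section 3.1 describes the data of this study as lying "beyond the 52 weeks of the parent Study M06-806", and Section 4.2 allows the extension to run for up to 408 weeks. Section 11.1 restricts the analysis to descriptive summaries, with all subjects in one group.

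**The concern.** Height and BMI both change with age in growing children. The plan puts one on an age-standardised scale and leaves the other raw, without giving a reason for the difference.

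In a randomised comparison, ordinary growth would largely cancel between arms. Here there is one arm, so nothing in the design removes it. A raw change at a given visit is the sum of the increase expected from age alone and any change in nutritional state, and the table cannot separate the two. A subject whose BMI falls behind that of peers can still show a positive change. Because the summary stands under Efficacy, a rising mean BMI could be read as nutritional recovery.

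**Working it through.** **Inputs from the SAP**
- Parent study before entry: 52 weeks (Section 3.1).
- Maximum extension: 408 weeks, described as about 8 years (Section 4.2).
- Week 408: nominal day 2857, window to Rx day 2941 (Section 6.0, Table 2).
- Age groups: under 13 years, and 13 years or older (Section 7.1).
- Continued growth is expected. Section 4.2 has a dosing provision for weight rising to 40 kg or more, and Table 1, footnote j, allows bone-age X-rays to be omitted once a subject is no longer growing.

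**The plan's own figures.** 408 × 7 / 365.25 = 7.8 years, which agrees with about 8 years. 408 × 7 + 1 = 2857, which agrees with Table 2.

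**Span of the BMI change.** (52 + 408) × 7 = 3220 days, and 3220 / 365.25 = 8.8 years. At the far edge of the last window, (364 + 2941) / 365.25 = 9.0 years. Some parts of the SAP use the word baseline for the Week 52 visit of M06-806, but the definition for change analyses in Section 6.0 is the pre-dose value of the parent study, so the 52 weeks count.

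**Growth part of the raw change.** The documents give no yearly BMI norm. That BMI rises with age through much of childhood and adolescence is taken as general knowledge, and the rate is an assumption:

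growth part = assumed yearly rise × years since the M06-806 baseline

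| Visit | Weeks from baseline | Years | 0.2 per year | 0.5 per year | 0.8 per year |
|---|---|---|---|---|---|
| Week 48 | 52 + 48 = 100 | 1.92 | 0.4 | 1.0 | 1.5 |
| Week 192 | 52 + 192 = 244 | 4.68 | 0.9 | 2.3 | 3.7 |
| Week 408 | 52 + 408 = 460 | 8.82 | 1.8 | 4.4 | 7.1 |

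(kg/m², no treatment effect.)

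The later rows are upper bounds, because they keep one rate for the whole period. A subject aged 13 at baseline would be 13 + 8.8 = 21.8 years old at Week 408. A subject whose age-related rise ended by Week 48 would carry only the Week 48 amount, 0.4 to 1.5 kg/m², at every later visit.

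**Masking.** Suppose peers gain 0.5 and a subject gains 0.3 kg/m² per year (both assumed). At Week 192 the table shows 0.3 × 4.68 = +1.4 kg/m², while peers have gained 0.5 × 4.68 = 2.3. The subject is 0.9 kg/m² behind but appears as a gain.

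**On the z-score scale.** A subject who keeps the same position relative to the age-and-sex reference has a change of 0 at every visit within the reference range, whatever the yearly rise.

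**The case against.** The strongest reply is that little hangs on this summary. Section 11.1 rules out inference, and its list of measures by which efficacy is evaluated does not include BMI. Section 4.5 does not define BMI as an efficacy variable, and the objective in Section 4.1 does not mention nutrition. This stands: no remission or response result changes, and the point is secondary. It does not remove the problem, because a descriptive table without a comparator depends on the scale of its variable to be readable.

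A second reply concerns size. The yearly rise is not in the documents, 8.8 years is a maximum, mean follow-up is not stated, and the plan itself expects some subjects to stop growing. This also stands. A reader might infer from the 460 weeks that subjects in general will drift by several kg/m², or that growth will necessarily look like a treatment gain. The documents support neither. They do not show how many subjects contribute at late visits, they fix no growth rate, and they nowhere say that a BMI rise is to be taken as benefit.

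Third, raw BMI may come from the protocol. Section 12.1 lists only one departure from it, unrelated to BMI. The protocol is not available here, so this stays open, but the SAP fixes the scale in its own text.

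Finally, a z-score has limits. The SAP names no growth reference and no rule for ages beyond its range, even for height. Subjects who reach adult age would have missing or capped z-scores, so raw BMI is still needed.

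**Conclusion.** The point holds as a limited one. Section 11.2 treats two growth-related measures differently in one sentence, and the raw BMI change, taken from the M06-806 baseline over at most 8.8 years in an uncontrolled paediatric group, can include normal age-related increase while subjects are still growing. It may be misread as nutritional benefit.

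The direction rests on the general fact that BMI rises with age in growing children. The size cannot be taken from the documents: the amounts tabulated above depend on the assumed rate, and those for late visits are upper bounds, smaller for older adolescents and for shorter follow-up. The PCDAI and CDAI summaries are unaffected. A change is worth making because the present scale is hard to interpret and the better one needs no new data, not because a main conclusion of the study is at risk.

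**What to change.** In Section 11.2:
- Add change from baseline in BMI-for-age-and-sex z-score over time, as the main BMI summary.
- Name the growth reference used for both the BMI and the height z-scores.
- State how visits at ages beyond the reference range are handled (missing or capped), with one rule for both measures, and report the number of subjects with a z-score at each visit.
- Keep the raw BMI summary alongside, including for subjects past the reference age.

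Height and weight are obtained at each office visit (Table 1, footnote c; Section 10.4), and age and sex are already held (Section 7.1), so no data need to be collected.

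The cost is one more derived variable, a few lines of SAP text, z-scores that are missing or capped at adult ages, and a BMI gain that may look smaller than on the raw scale. The z-score removes the age trend only. Without a comparator, a change in it is still not by itself evidence of a treatment effect, and the report should say so.
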